12.5	Temporary halt and (prematurely) end of study report.....	29
12.6	Public disclosure and publication policy	29
13.	STRUCTURED RISK ANALYSIS.....	31
13.1	Potential issues of concern.....	31
13.2	Synthesis	31
14.	Appendices	32
15.	References	32

LIST OF ABBREVIATIONS AND RELEVANT DEFINITIONS

ABR	General Assessment and Registration form (ABR form), the application form that is required for submission to the accredited Ethics Committee; in Dutch: Algemeen Beoordelings- en Registratieformulier (ABR-formulier)
AE	Adverse Event
AR	Adverse Reaction
ASA	ASA Physical Status Classification System
BAC	Blinded Adjudication Committee
CA	Competent Authority
CCMO	Central Committee on Research Involving Human Subjects; in Dutch: Centrale Commissie Mensgebonden Onderzoek
CV	Curriculum Vitae
DSMB	Data Safety Monitoring Board
GCP	Good Clinical Practice
GDPR	General Data Protection Regulation; in Dutch: Algemene Verordening Gegevensbescherming (AVG)
iAEs	Intra-operative Adverse Events
IC	Informed Consent
METC	Medical research ethics committee (MREC); in Dutch: medisch-ethische toetsingscommissie (METC)
NMB	Neuromuscular block
PTC	Post Tetanic Count
(S)AE	(Serious) Adverse Event
Sponsor	The sponsor is the party that commissions the organisation or performance of the research, for example a pharmaceutical company, academic hospital, scientific organisation or investigator. A party that provides funding for a study but does not commission it is not regarded as the sponsor, but referred to as a subsidising party.
TIVA	Total intravenous anesthesia
TOF	Train of Four
UAVG	Dutch Act on Implementation of the General Data Protection Regulation; in Dutch: Uitvoeringswet AVG
NRS	Numeric Rating Scale
WMO	Medical Research Involving Human Subjects Act; in Dutch: Wet Medisch-wetenschappelijk Onderzoek met Mensen

SUMMARY

Rationale: Muscle relaxants are routinely applied during anesthesia to facilitate endotracheal intubation and to improve surgical working conditions. Several investigations have shown that a deep neuromuscular block (NMB) improves the surgical working conditions over a standard NMB and effectively precludes sudden deterioration of the surgical field. However, whether the improvement of surgical working conditions translates into less intra- and postoperative complications remains uncertain. Small prospective or retrospective studies shown an decrease of the incidence of intraoperative adverse events and postoperative complications after a deep NMB. There is a need to confirm these outcome data prospectively, in a large number of patients and clinics and during a variety of surgical procedures.

Objective: To study the effect of deep neuromuscular block as compared to standard neuromuscular block on intra-operative adverse events during laparoscopic surgery.

Study design: Multi center, randomized controlled clinical trial

Study population: 922 patients planned for elective laparoscopic abdominal surgery.

Intervention: Patients will be randomized between a deep NMB (group 1; aimed at PTC 1-2) and standard care (group 2; standard care NMB).

Main study parameters/endpoints: Primary endpoint is the difference in incidence of intra-operative adverse events during laparoscopic surgery graded on the CLASSIC scale (*ie.* CLASSIC grade ≥ 2) between both groups

Secondary endpoints include the surgical working conditions, 30 day post-operative complications and quality of recovery.

Nature and extent of the burden and risks associated with participation, benefit and group

relatedness: The aim of this study is to compare two targets of neuromuscular block that are currently interchangeably used (both deep and standard NMB are routine practice at the LUMC).

Additionally, all other anesthesia and surgery related procedures (*eg.* medication and monitoring) follow routine practice. We therefore anticipate no additional risks from study related procedures.

Before surgery a Quality of Recovery and Short Form Health Survey will be obtained. After surgery the QoR-40 will be repeated twice, and the SF-36 will be obtained at 30 days after surgery.

1. INTRODUCTION AND RATIONALE

Muscle relaxants (*ie.* neuromuscular blocking agents; NMBAs) are routinely applied during anesthesia to facilitate endotracheal intubation and to improve surgical working conditions. However, as NMBAs have relatively long half lives, the dosing of these agents is often restricted in clinical practice.

Incomplete recovery of neuromuscular block (NMB) is associated with postoperative adverse events and should therefore be avoided at all costs. Hence, in standard clinical practice, NMB is often instituted only at the induction of anesthesia and hereafter allowed to recover spontaneously to limit the chance of residual NMB. Surgical procedures however have evolved to become increasingly complex. For instance, robotic surgery and increasingly complex laparoscopic surgery are now routinely performed. These types of surgery demand optimal working conditions to be successful and the standard use of NMBAs in these procedures may not be sufficient. Indeed, several investigations have shown that a deep neuromuscular block (*ie.* Post-tetanic-count of 1-2 twitches; PTC 1-2) during these procedures 1-2 twitches) improves the surgical working conditions over a standard NMB (*ie.* Train-of-four count > 0 twitches; TOF 1-3) and effectively precludes sudden deterioration of the surgical field.[1-8] Additionally, deep NMB has become feasible due to the availability of the selective reversal agent sugammadex. Sugammadex ensures quick and safe recovery of any depth of NMB and prevents residual NMB.[9] However, whether the use of a deep NMB translates into less intra- and postoperative complications remains uncertain. A recent retrospective analysis of neuromuscular management during laparoscopic retroperitoneal surgery showed a reduced rate of unplanned 30 day readmissions when a deep NMB over a moderate NMB was applied (3.8% vs. 12.7%).[10] In addition, a pooled analysis of 4 randomized controlled trials comparing different levels of intra-abdominal pressure and neuromuscular blockade during laparoscopic donor nephrectomy, showed a significant reduction in the incidence of intra-operative surgical complications from 12.6% with moderate NMB to 4.8% with deep NMB. [11-14] These previous observations were made in small prospective or retrospective studies. There is a need to confirm these outcome data prospectively, in a larger prospective trial for a variety of surgical procedures. We therefore propose a multi-center, randomized controlled trial, to study the effect of a deep NMB (PTC 1-2 twitches) versus standard NMB (single induction dose rocuronium) in a variety of laparoscopic surgical procedures on the incidence of intraoperative adverse events and postoperative outcome data.

2. OBJECTIVES

Primary Objectives:

To study the effect of deep neuromuscular block compared to standard neuromuscular block on intra-operative adverse events during laparoscopic surgery using the CLASSIC score system; see Table 2.

Secondary Objectives:

To study the effect of deep neuromuscular block as compared to standard neuromuscular block on:

- Surgical working conditions (using the validated Leiden surgical rating scale: L-SRS, Table 3)
- 30-day post-operative complications (using the Clavien-Dindo classification, Table 6)
- 30-day post-operative complications according to the Comprehensive Complication Index (<https://www.assesssurgery.com/>)
- 30-day unplanned readmission rates
- Quality of recovery at post-operative day 1, 2 and 30 after laparoscopic surgery.
 - Quality-of-recovery (QoR-40 questionnaire at postoperative day 1 and 2 (Appendix 1))
 - Quality-of-life at postoperative day 30 (SF36 questionnaire, Appendix 2)

Primary hypothesis:

Deep neuromuscular blockade reduces the incidence of intra-operative adverse events as measured by the CLASSIC score during laparoscopic surgery as compared to standard neuromuscular blockade.

Secondary hypotheses:

Deep neuromuscular blockade improves surgical working conditions and the early quality of recovery and reduces 30-day post-operative complications and unplanned readmissions after laparoscopic surgery, as compared to standard neuromuscular blockade.

3. STUDY DESIGN

The EURO Relax is a multi-center, randomized controlled trial in patients undergoing laparoscopic abdominal surgery. Patients undergoing elective laparoscopic surgery in different fields of abdominal surgery will be randomized 1:1 in blocks of 2 and 4 to the deep or standard neuromuscular block group. Randomization will be stratified per center and BUPA category (MAJOR, MAJOR PLUS or COMPLEX MAJOR; for examples see table 1).

Patient inclusion will occur competitively in each center. Due to differences in inclusion rate, final inclusion could differ slightly in comparison with the proposed inclusion number per center.

[figure not shown]

Figure 1. Inclusion flowchart EURO Relax study. QoR: *quality of recovery*; *iAE*: *intraoperative adverse event*; L-SRS: *Leiden Surgical Rating Scale*; CCI: *composite complication index*.

4. STUDY POPULATION

4.1 Population (base)

922 ASA class 1-3, aged > 18 years, scheduled for elective laparoscopic abdominal surgery (such as, but not restricted to upper gastrointestinal tract-, lower gastrointestinal tract-, urological- and gynecological surgery)

4.2 Inclusion criteria

In order to be eligible to participate in this study, a patient must meet all of the following criteria:

- Patients scheduled for elective laparoscopic abdominal procedure with a complexity according to the BUPA classification for case complexity: 'MAJOR', 'MAJOR PLUS' or 'COMPLEX MAJOR'. Several examples of eligible procedures are stated in Table 1. Procedures not listed in Table 1 that are of listed in <https://codes.bupa.co.uk/procedures> as a Surgeon's Category \geq 'Major 3', can be enrolled to the trial. The BUPA class of the specific procedure is listed under BUPA hospital category.
- ASA class I-III
- \geq 18 years of age
- Ability to give oral and written informed consent

Table 1. Examples of cases with BUPA classification for case complexity major, major plus or complex major used for the Classic validation study. (with permission of dr. [name] (principle investigator of the CLASSIC validation study; NCT03009929).

• BUPA MAJOR:	-cholecystectomy
• BUPA MAJOR PLUS:	-colorectal resection -nephrectomy -hysterectomy -adrenalectomy (uni) -right colectomy -partial nephrectomy -gastric sleeve -gastric bypass -donor nephrectomy -left colectomy -sigmoidectomy -laparoscopic partial stomach resection -myomectomy

• BUPA COMPLEX MAJOR:	
-low anterior resection-partial hepatectomy-prostatectomy-hemi hepatectomy-esophagostomy-laparoscopic pyeloplasty-laparoscopic stomach resection-total cystectomy
---	--

4.3 Exclusion criteria

- Low or intermediate complexity laparoscopic procedures (BUPA 'SIMPLE' or 'INTER')
- Known or suspected neuromuscular disorders impairing neuromuscular function
- Allergies to muscle relaxants, anesthetics or narcotics mentioned in paragraph 8.3
- A (family) history of malignant hyperthermia
- Women who are or may be pregnant or are currently breast feeding
- Chronic use of any type of opioid or psychotropic drug for the treatment of chronic pain
- Use of NSAID's shorter than 5 days before surgery for the treatment of chronic pain
- Indication for rapid sequence induction
- Contra-indication for sugammadex use (e.g. known sugammadex allergy or GFR<30 ml/min)

4.4 Sample size calculation

Preliminary data of the CLASSIC validation study as confidentially provided by dr. [name] (principle investigator; NCT03009929) confirm that the incidence of GRADE ≥ 2 iAEs (Table 2) is 20% for BUPA categories (unpublished data).

Table 2. Adapted version of the CLASSIC classification for intra-operative adverse events (*with permission of dr. [name] (principle investigator of the CLASSIC validation study; NCT03009929).*

Grade 0	No deviation from the ideal intraoperative course
Grade 1	Any deviation from the ideal intraoperative course without the need for any additional treatment or intervention; patient asymptomatic or mild symptoms
Grade 2	Any deviation from the ideal intraoperative course with the need for any additional minor treatment or intervention; patient with moderate symptoms, not life-threatening and not leading to permanent disability
Grade 3	Any deviation from the ideal intraoperative course with the need for any additional moderate treatment or intervention; patient with severe symptoms, potentially life-threatening and/or potentially leading to permanent disability
Grade 4	Any deviation from the ideal intraoperative course with the need for any additional major treatment or intervention; patient with life-threatening symptoms and/or leading to permanent disability
Grade 5	Any deviation from the ideal intraoperative course with intraoperative death of the patient

The following events are not defined as intraoperative complications: sequelae, failures of cure, events related to the underlying disease, wrong-site or wrong-patient surgery or errors in indication

- To date, the minimal clinically important difference (MCID) for intra-operative adverse events according to the CLASSIC classification has not been published. We consider a relative reduction in intra-operative adverse events, CLASSIC grade ≥ 2 , of 40% a clinically relevant difference. As de-

scribed above the reported average rate of grade 2 intra-operative Adverse Events (iAEs) is 20%.

- With an alpha of 5% and beta of 90%, 439 patients are required in each arm of the study (in total 878 patients).
 - Assuming a 5% rate of drop-out a total of 922 patients should be randomized 1:1 in this study. Reasons for drop-out are:
 - conversion to open surgery within the first 20 minutes of the procedure due to unforeseen adhesions, tumor progression, (peritoneal) metastases or other diagnosis
 - pre-incision alteration of surgical plan to laparotomy instead of laparoscopy after patient randomization to deep NMB or standard-of-care group
 - patient safety concerns at induction of anesthesia, e.g. anaphylaxis at induction of anesthesia or unanticipated difficult airway
 - Patients with a conversion to deep NMB due to intra-operative adverse events will not be excluded.

4.5 Pre-study requirements

There are no specific study requirements.

5. TREATMENT OF SUBJECTS

There are no specific study-related pre-study requirements. On the day of surgery, patients will be randomized between the two treatment groups. Anesthesia and postoperative care follow routine local protocol, apart from neuromuscular management. Neuromuscular management during surgery depends on the treatment allocation; patients will be randomized between one of the following groups:

Group 1 (experimental): Deep neuromuscular block.

- Muscle relaxation with rocuronium (Esmeron, MSD BV), target depth: post-tetanic-count of 1-2 twitches from start of surgery until the end
- Induction dose rocuronium: 0.6 – 1.0 mg/kg, aimed at PTC 1-2 at surgery start
- Maintenance: continuous infusion of rocuronium at 0.2-0.6 mg/kg/hr, titrated to maintain PTC 1-2
- Reversal of NMB with sugammadex 4 mg/kg at the end of surgery

Group 2 (comparator): standard care

- Muscle relaxation with rocuronium (Esmeron, MSD BV), target depth: train-of-four count of > 0 twitches from start of surgery until the end.
- Induction dose rocuronium: 0.3-0.6 mg/kg, aimed at a TOF count of > 0 twitches at surgery start
- Repeated doses of rocuronium 10 mg on request by the surgeon only
- Reversal of NMB with sugammadex 2 mg/kg at the end of surgery, when TOF ratio < 0.9 at surgery end.

5.1 Investigational treatment

Not applicable.

5.2 Use of co-intervention

Not applicable

5.3 Escape medication

Not applicable

6. INVESTIGATIONAL PRODUCT

Not applicable.

7. NON-INVESTIGATIONAL PRODUCT

Not applicable.

8. METHODS

8.1 Study parameters/endpoints

Main study parameter/endpoint

Incidence of intra-operative adverse events during laparoscopic surgery (CLASSIC grade ≥ 2 , Table 2) in both groups

8.1.1 Secondary study parameters/endpoints

To study the effect of deep neuromuscular block as compared to standard neuromuscular block on:

- Surgical working conditions (L-SRS, Table 3)
- 30-day post-operative complications (Clavien-Dindo, Table 6)
- 30-day post-operative complications according to the Comprehensive Complication Index
- 30-day unplanned readmission rates
- Quality of recovery at post-operative day 1, 2 and 30 after laparoscopic surgery.
 - Quality-of-recovery (QoR-40 at postoperative day 1 and 2; Aldrete score (Table 5) at the PACU)
 - Quality-of-life at postoperative day 30 (SF36, Appendix 2)

8.1.2 Other study parameters

- Patient age, gender, length and weight, ASA class, underlying disease(s), planned procedure, blood pressure and heart rate, center of admission
- Pre-operative NRS, QoR-40 and SF 36
- Per operative the following variables will be noted, after installation of the pneumoperitoneum at 15 minute intervals until the end of the surgery. At these moments the L-SRS is also scored:
 - Heart rate (/min), blood pressure in mmHg
 - Intra-abdominal pressure in mmHg and total insufflations volume (in Liters)
 - Depth of anesthesia: Bispectral Index and end-tidal sevoflurane
 - Depth of NMB (TOF count and/or PTC)
 - Duration of surgery and anesthesia
 - Time of extubation
 - Cumulative drug dosages (propofol, opioids, muscle relaxant, reversal agent, inotropics, NSAIDS's or metamizol)
 - Core temperature in degrees Celsius
 - Surgical satisfaction with the anesthesia: 'very dissatisfied', 'dissatisfied', 'satisfied' tot 'very satisfied'.
- Postoperative recovery scores:
 - Time to discharge readiness (Aldrete score ≥ 9 and NRS < 5)
 - Heart rate (/min), blood pressure in mmHg
 - peripheral oxygen saturation, respiratory rate (/min), use of supplemental O₂ (in liters/minute)
 - NRS and administration of analgesic medication
 - Ramsay sedation scale and Aldrete score
 - Nausea or vomiting

- Length of admission at the PACU and/or ICU (if applicable) and duration of hospital admission
 - Pain scores (numeric rating scale; NRS 0 no pain – 10 worst pain imaginable) at movement (and rest) three times daily until discharge or to a maximum of 72 hours will be extracted from the patient clinical charts.
 - Medication use (three times daily until discharge or to a maximum of 72 hours) will be extracted from the patient clinical charts.
 - Cumulative opiate use
 - Cumulative use of other analgesics and anti-emetics

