All patients will receive neuromuscular monitoring according to international guidelines for neuromuscular monitoring in research.[15] Neuromuscular monitoring will exclusively be applied at the m. adductor pollicis of one of the free moving thumbs. The following devices are allowed in this study: TOF-scan, Idmed, France, CE 0459 TOF-Watch, Organon, Ireland, CE 0543; or electromyography; GE NMT, GE-healthcare, Finland, CE 0537 .

All monitors will be applied in accordance with the guidelines of the manufacturer, including any baseline and calibration procedures; these will take place after the patient has been put under general anesthesia, but before the administration of any NMBA. Baseline TOF ratio will be noted in the CRF. All monitor types can be used interchangeably in practice of this study. Patients may only be extubated when the TOF ratio is at least 0.9.

Surgical procedures: All laparoscopic procedures will exclusively be performed at standard insufflation pressures (IAP 12 mmHg). After insufflation, intra- abdominal volume will be recorded. This provides an indirect measure of abdominal wall compliance and workspace.

Intra operative scoring procedures

Intra operative adverse events

Intra operative adverse events will be scored using the CLASSIC score (see table 2). This score has recently been developed and validated in a Delphi study (NCT03009929). Scoring of the CLASSIC scale

will be done by the blinded surgeon and blinded attending anesthesiologist (based on consensus) at the end of every procedure. Notably, the unblinded researcher on the OR is NOT involved in the scoring. CLASSIC classification is only applicable for events that have occurred *during* the procedure, any adverse event at PACU and beyond will be scored using Clavien Dindo scale (see table 6).

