10.2 Secondary study parameters

Continuous normally distributed variables will be expressed by their mean and standard deviation or when not normally distributed as medians and their interquartile ranges. Categorical variables will be expressed as n (%). To test groups Student's t test will be used, if continuous data are not normally distributed the Mann-Whitney U test will be used. Categorical variables will be compared with the Chi-square test or Fisher's exact tests. P-values < 0.05 will be considered significant for the primary outcome. A cut off p-value of < 0.01 will be applied for secondary outcomes.

Data analysis will be performed using R Studio, Boston, MA, USA..

Longitudinal data (heart rate, blood pressure, L-SRS, BIS levels compared to the depth of NMB at the given moment) will be analyzed using linear mixed models. NONMEM (ICON Development Solutions, Ellicott, MD, USA), will be used for statistical analysis.

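### Depth of block is recorded during surgery only as TOF count and/or PTC, so every state after the fourth twitch is stored as 4 and light block in the standard arm is not resolved

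*Combined protocol and SAP*

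**What the plan says.** Section 8.1.2 lists the variables noted "after installation of the pneumoperitoneum at 15 minute intervals until the end of the surgery". The depth item in that list is "Depth of NMB (TOF count and/or PTC". The TOF ratio is not in the list. It appears in three other places:

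- Section 8.3, before any relaxant is given: "Baseline TOF ratio will be noted in the CRF".
- Section 5, Group 2: "Reversal of NMB with sugammadex 2 mg/kg at the end of surgery, when TOF ratio < 0.9 at surgery end".
- Section 8.3, as the extubation threshold of at least 0.9.

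Of these, only the baseline value is explicitly sent to the CRF, and none is a repeated intra-operative measurement.

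For Group 2, section 5 sets "target depth: train-of-four count of > 0 twitches from start of surgery until the end" and "Repeated doses of rocuronium 10 mg on request by the surgeon only". Section 1 says of usual practice that "NMB is often instituted only at the induction of anesthesia and hereafter allowed to recover spontaneously", and describes the trial's comparator as one induction dose. Section 1 also labels standard block as TOF 1-3.

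Section 10.2 plans linear mixed models for the longitudinal data (heart rate, blood pressure, L-SRS and "BIS levels compared to the depth of NMB at the given moment"). It does not say how PTC and TOF count combine into one depth variable.

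**The concern.** A train-of-four has four stimuli, so its count runs from 0 to 4. Once the fourth twitch returns, further recovery shows only in the TOF ratio. The intra-operative record omits the ratio, so a patient with four weak twitches and a patient with no remaining block get the same entry.

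Two uses of the data are touched. The first is the section 10.2 model, which has no depth contrast above the fourth twitch. That end of the scale matters because L-SRS, the first-listed secondary endpoint, defines its poorer grades by inadequate relaxation, contractions and movement. The second is the description of the block delivered in the standard arm, and so of the contrast the trial tested. A ratio that was not recorded at the time may not be recoverable later.

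**Working it through.** The plan gives no figure for the depth model, so there is none to reproduce here. Its one calculated figure, the sample size, concerns the primary endpoint and does not involve measured depth.

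**1. Can the record separate states above the fourth twitch?** No. The count has a maximum of 4, PTC applies when the count is 0, and the ratio is not among the 15-minute variables.

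**2. Does the plan allow Group 2 into that range?** Yes. The target is a count above 0 with no upper limit, and repeat doses are given only on request. Making reversal conditional on a ratio below 0.9 makes sense only if some patients may finish at 0.9 or above. The TOF 1-3 label in section 1 points the other way, and the documents do not reconcile the two.

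**3. How many readings would be at the ceiling?** The documents give no recovery times, no interval from induction to pneumoperitoneum and no duration of surgery. As an illustration only, assume that:

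- pneumoperitoneum starts 30 min after induction;
- duration is counted from that point;
- no repeat dose is given;
- the fourth twitch returns at time T after induction.

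Records fall at 30, 45, 60, ... min. The number of records is duration/15 + 1, which is 5, 9 or 13 for 60, 120 or 180 min. The share at the ceiling is the number of records later than T divided by that total.

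| Duration | T = 30 | T = 45 | T = 60 | T = 90 |
|---|---|---|---|---|
| 60 min | 4/5 = 80% | 3/5 = 60% | 2/5 = 40% | 0/5 = 0% |
| 120 min | 8/9 = 89% | 7/9 = 78% | 6/9 = 67% | 4/9 = 44% |
| 180 min | 12/13 = 92% | 11/13 = 85% | 10/13 = 77% | 8/13 = 62% |

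Repeat doses would lower these shares.

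**4. How much depth information would be lost within the standard arm?** This is again an illustration. Let q be the share of readings at count 4. Let the other readings be uniform on 1, 2, 3 (mean 2, variance 2/3). Let the ratio be uniform on 0.05 to 1 (mean 0.525, variance 0.95²/12 = 0.0752). Let true depth above the fourth twitch be 4 + k × ratio, where k is the width of that range in count-steps. Then:

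- Var(recorded) = (1−q)(2/3) + q(1−q)·2²
- Var(true) = (1−q)(2/3) + q·k²·0.0752 + q(1−q)(2 + 0.525k)²
- Cov = (1−q)(2/3) + q(1−q)·2·(2 + 0.525k)
- share of variance kept = Cov² / [Var(recorded) × Var(true)]

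Mildest case, q = 0.1 and k = 1: 1.0545² / (0.960 × 1.181) = 0.98.

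Worst case, q = 0.9 and k = 4: 0.8047² / (0.4267 × 2.6625) = 0.57.

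| q | k = 1 | k = 2 | k = 4 |
|---|---|---|---|
| 0.1 | 0.98 | 0.94 | 0.84 |
| 0.5 | 0.97 | 0.92 | 0.83 |
| 0.9 | 0.90 | 0.76 | 0.57 |

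The loss therefore runs from negligible to large, depending on inputs that the documents do not supply.

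**The case against.** The strongest reply is that little depends on this. Depth of block sits under other study parameters. The section 10.1 chi-square test and the randomised between-arm secondary comparisons do not use measured depth. The affected model is a non-randomised, exposure-type analysis, and the wording of section 10.2 leaves open whether depth is to be related to BIS alone or to the whole list of longitudinal variables. Section 1 also places standard block at TOF 1-3, wholly inside the recorded range. All of this stands and limits the severity.

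A reader might infer three stronger things that the documents do not support:

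- **That the depth model cannot see the standard arm.** Counts 0 to 3 and arrival at 4 are recorded, and count 4 remains distinct from the PTC levels of deep block. Four weak twitches are also not close to deep block on the protocol's own scale, because counts 1 to 3 lie between.
- **That standard-arm depth would be a constant 4 for much of the operation.** The shares of 0% to 92% above rest wholly on assumed times, and section 5 and section 8.3 both allow further rocuronium.
- **That nothing can be said about residual block.** Cumulative reversal-agent dose is recorded under section 8.1.2. If the Group 2 rule is followed, whether sugammadex was given shows on which side of 0.9 the ratio lay at the end of surgery. That is one binary reading and not a time course, but it is some information.

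None of this removes the omission itself. No section provides for the ratio to be recorded during surgery.

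**Conclusion.** The point holds as a ceiling on the intra-operative depth scale. All states after the fourth twitch are stored as 4, and the plan allows Group 2 to reach them. The consequence is confined to resolution at light block in the secondary longitudinal model and in the description of the delivered standard-arm block. The primary result and the randomised comparisons are untouched.

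The size cannot be computed from the documents. Under the stated assumptions, 0% to 92% of standard-arm readings would be at the ceiling, and the recorded count would keep 98% down to 57% of the variance in true depth. Severity is minor. It is worth acting on because the loss may be irrecoverable and the remedy is cheap.

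**What to change.** In section 8.1.2, replace the depth item with a rule that leaves one value per time point: PTC when the TOF count is 0, the TOF count when it is 1 to 3, and the TOF ratio when the count is 4.

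In section 10.2, state which outcomes are related to depth, and enter depth as one pre-specified ordered categorical factor: PTC levels, then TOF counts 1 to 3, then TOF-ratio bands. Fix the band cut-points before analysis, with the top band at 0.9 or above, the threshold the protocol already uses.

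The cost is one more eCRF value at records where the count is 4, and a depth factor with more levels, some of which may be sparse. The monitor is already attached and already has to yield a ratio at baseline and before extubation, and section 8.2 places an unblinded researcher responsible for the block at every procedure. Dosing, reversal and blinding do not change.
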